#### 9.2.5.6. Incomplete dates for last treatment administration

Scenario 1: If the last treatment administration date is completely missing and there is no study treatment discontinuation (STD) page and no death date:

• The subject should be treated as on-going and use the cutoff date as the last dosing date up to date.

Scenario 2: If the last treatment administration date is completely or partially missing and there is either STD page or death date available:

If only Year is available and Year < Year of min (DISC date, death date);

Imputed date= Dec31yyyy

If both Year and Month are available, Year = Year of min(DISC date, death date) and Month < the month of min(DISC date, death date)

Imputed date= last day of the Month

All other cases imputed date= min (DISC date, death date)

The imputed date will be compared with start date of treatment. If the imputed date is < start date of treatment, set the last treatment administration date to be the treatment start date; otherwise use the imputed date.

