#### Post therapies

#### • Start date:

- If Day is missing, then impute to the max (reference start date, first day of the month).
- Day and month are missing then impute to the max(reference start date, Jan 1)
- $\circ$  Reference start date will be last date of study treatment administration + 1.
- End date: No imputation

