# 9.3. Study Time Periods

#### 9.3.1. Time in Relation to Treatment

Adverse events, serious adverse events, death, laboratory data, vitals, ECG, and ECHO/MUGA will be assigned to the study time periods defined below. Partial dates will be imputed into full dates, if applicable, for slotting data to the appropriate categories below (see Section 9.2.5). Flag variables (time in relation to study treatment) indicating the study time periods will be added to these datasets.

The overall observation period will be divided into three mutually exclusive segments:

**Pre-therapy** is defined as the time prior to the subject's first dose of study treatment.

**On-therapy** is defined as the time from first dose of study treatment to the date of the last dose of study treatment + 28 days.

**Post-therapy** is defined as any time beyond the on-therapy period.

Some datasets include the first dose day as On-therapy and some exclude the first dose date as On-Therapy. The first dose day (Day 1) is considered pre-therapy for ECOG, ECG, vital signs, liver events, lab tests, and cardiac scan. The first dose day (Day 1) is considered to be on-therapy for adverse events and concomitant medications.

All safety data (including those from the post-therapy period) will be listed and those occurring during the pre-therapy and post-therapy periods are to be flagged.

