# 11.1. Extent of Exposure

The duration of exposure to Pazopanib in days (from first day to last day of treatment) will be summarised by cohort. Descriptive statistics including mean, median, standard deviation, minimum, and maximum will be calculated for time on study treatment. Exposure categories (in weeks) will also be summarized.

Average daily dose will be calculated as Cumulative dose (mg) / Duration of exposure to study treatment (day), and summarized by cohort, using the mean, standard deviation, median, minimum, and maximum. Actual duration of exposure will be calculated as the date of last dosing-date of first dosing+1.

Study drug dose received will be summarized by cohort. Cumulative dose, actual dose intensity and relative dose intensity will be presented. Actual dose intensity will be calculated as actual total dose/actual duration of exposure. Relative dose intensity will be calculated as (actual dose intensity/planned dose intensity)\*100. Planned dose intensity will be calculated as planned total dose/planned duration of exposure, where planned duration of exposure will be the same as actual duration of exposure.

A by-subject listing of data on subject exposure including dose reduction, dose interruptions and the corresponding reasons will be produced.

The safety population will be used for all summaries and listing of study treatment.

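### The SAP's rule for a partial last-dose date has no branch for a known month in an earlier calendar year, so the imputed date contradicts the recorded month (minor)

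*SAP*

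**What the plan says.** Scenario 2 of SAP 9.2.5.6 covers this situation: "If the last treatment administration date is completely or partially missing and there is either STD page or death date available". Write D for the earlier of the discontinuation and death dates. The rule has three outcomes:

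- **Branch 1.** "If only Year is available and Year < Year of min (DISC date, death date"), then "Imputed date= Dec31yyyy".
- **Branch 2.** "If both Year and Month are available, Year = Year of min(DISC date, death date"), with the recorded month before the month of D. The result is the last day of the recorded month.
- **Catch-all.** "All other cases imputed date= min (DISC date, death date").

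One check follows: a result before treatment start is raised to the treatment start date. Nothing compares the result with the recorded month.

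The last-dose date is used in several places. In SAP 9.3.1 the on-therapy period "is defined as the time from first dose of study treatment to the date of the last dose of study treatment + 28 days". In SAP 11.1 the duration of exposure runs from first to last dose, and "Actual dose intensity will be calculated as actual total dose/actual duration of exposure". SAP 11.4 classifies deaths as within or beyond 28 days of the last dose. In SAP 9.2.5.4, for partial start dates of post-study anti-cancer therapy, "Reference start date will be last date of study treatment administration + 1".

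**The concern.** Branch 1 keeps the imputed date inside the recorded year, and Branch 2 keeps it inside the recorded month. A date with a known month in an earlier year gets neither protection. It is moved to D, in a month that the case report form rules out. The rule is also inconsistent with itself, because adding the month to a known year moves the imputed date later.

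A last-dose date that is too late lengthens exposure, lowers average daily dose and dose intensity, and extends the on-therapy period. Cohorts have 10 patients per stage (SAP section 3), so a single misdated patient can show in a cohort's exposure summary.

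**Working it through.** The plan states no figure on this point, so there is none to reproduce. The check applies the three branches literally and compares them with a rule that uses the end of the recorded month whenever that month precedes the month of D.

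**Inputs.** The branches and the treatment-start floor come from SAP 9.2.5.6, the 28-day window from SAP 9.3.1 and the exposure formula from SAP 11.1. Treatment start on 1 June 2017 and the dates below are assumptions for illustration.

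**Logic for DEC2017 with D = 20 Jan 2018.** Branch 1 fails because the month is known. Branch 2 fails because 2017 is not 2018. The catch-all gives 20 Jan 2018. The floor at treatment start cannot correct a date that is too late.

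**Formulas.** Overshoot = D minus the last day of the recorded month. Exposure = last dose minus first dose + 1. On-therapy end = last dose + 28 days.

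| Recorded last dose | D | Rule as written | End of recorded period | Overshoot (days) |
|---|---|---|---|---|
| 2017 only | 20 Jan 2018 | 31 Dec 2017 | 31 Dec 2017 | 0 |
| DEC2017 | 20 Jan 2018 | 20 Jan 2018 | 31 Dec 2017 | 20 |
| DEC2017 | 2 Jan 2018 | 2 Jan 2018 | 31 Dec 2017 | 2 |
| NOV2017 | 20 Jan 2018 | 20 Jan 2018 | 30 Nov 2017 | 51 |
| NOV2017 | 20 Dec 2017 | 30 Nov 2017 | 30 Nov 2017 | 0 |

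The first two rows show the inconsistency: the less complete date gives the earlier result. The last row shows the rule working when there is no change of year.

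**Range over every January 2018 value of D.** For December the overshoot is 1 to 31 days, and 14 days or more for 18 of the 31 dates. For November it is 32 to 62 days, and for October 62 to 92. These are lower bounds on the distance from the true last dose, which lies on or before the last day of the recorded month.

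**Effect on outputs, DEC2017 with D = 20 Jan 2018.**
- Exposure is 234 days as written and 214 days using the end of the month.
- For a given cumulative dose, average daily dose and dose intensity are 214/234 = 91% of the value under the repaired rule.
- The on-therapy period ends on 17 Feb 2018 rather than 28 Jan 2018.
- A death on 10 Feb 2018 (assumed) would be 21 days after the last dose as written, hence within 28 days. Under the repaired rule it would be 41 days after, hence beyond.

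For NOV2017 with the same D, exposure is 234 against 183 days, a ratio of 78%.

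**The case against.** The strongest reply is that the case is rare and its reach is short. Most of that stands.

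- **Frequency.** The rule is triggered only by a missing day, a known month and a change of calendar year before D. Patient diaries record each dose date (Protocol Appendices IA and IB), and returned drug is reconciled with the eCRF (Protocol 6.1). The documents identify no affected patient.
- **Size of the gap.** A reader might infer that the error is always weeks, or that treatment holds of up to 28 days make a November-to-January gap likely. They do not: 30 November to 1 January is 32 days, as is 31 December to 1 February. Protocol 4.1.3 calls for permanent discontinuation after more than 28 days' interruption. A hold of that length supports only December to January, where the overshoot can be a day or two. Longer gaps need a late-dated discontinuation page, which the documents do not show.
- **Adverse events.** A reader might infer that many post-therapy events would enter the on-therapy tables. Protocol 8.2 and section 11 collect AEs and SAEs routinely only to 28 days after the last dose, with narrow exceptions. SAP 11.2 summarises treatment-related AEs regardless of window. What remains is late laboratory and ECG values, any late-recorded events, and the split of deaths.
- **Time-to-event endpoints.** A reader might infer that this date drives PFS, TTP and DoR censoring. It enters only when the start of new anti-cancer therapy is itself a partial date, and it matters only if an assessment or event falls between the candidate dates.

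SAP 9.2 also refers to separate dataset specifications, which are not among the documents and might handle the case. That does not repair the SAP text, which states a rule for all other cases and so gives a definite, wrong result.

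**Conclusion.** The gap is real and follows from the SAP text alone. A last-dose date with a known month in an earlier year is set to the discontinuation or death date, against the recorded month. The overshoot is 1 to 31 days for December with a January discontinuation or death, and at least 32 days for November or earlier.

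Severity is minor. The number of affected patients is not given and is probably small. The effect is on descriptive exposure and dose-intensity summaries, the on-therapy cut-off, and the classification of deaths at 28 days. The documents do not support reading this as a threat to the efficacy conclusions. Objective response and the two-stage rule do not use the date, no formal hypothesis is tested (SAP 8.4), and the study had already been declared futile after stage 1 (SAP 4.3).

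The day counts follow from the calendar and the stated rule. The exposure, dose-intensity and death examples rest on the assumed dates.

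**What to change.** Reword Branch 2 of Scenario 2 so that it applies whenever year and month are both recorded and that year-month comes before the year-month of the earlier of the discontinuation and death dates, whether in the same calendar year or an earlier one. The imputed date is then the last day of the recorded month. Leave Branch 1, the catch-all and the treatment-start floor unchanged. Check that the dataset specifications carry the same rule.

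The cost is one sentence in the SAP and one condition in the derivation code. No case that the present Branch 1 or Branch 2 already handles would change.

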#### 9.2.5.7. Assessment date of tumor assessments

All investigation dates (e.g. X-ray, CT scan) must be completed with day, month and year.

If one or more investigation dates are incomplete but other investigation dates are available, this/these incomplete date(s) are not considered for calculation of the assessment date and assessment date is calculated as the latest of all investigation dates (e.g. X-ray, CT-scan) if the overall lesion response at that assessment is CR/PR/SD/UNK. Otherwise – if overall lesion response is progression – the assessment date is calculated as the earliest date of all investigation dates at that evaluation number. If all measurement dates have no day recorded, the 1st of the month is used.

If the month is not completed, for any of the investigations, the respective assessment will be considered to be at the date which is exactly between previous and following assessment. If a previous and following assessment is not available, this assessment will not be used for any calculation.

### 9.2.6. Handling of concentrations below LLOQ or missing

Missing values of concentrations will not be imputed. When summarizing concentrations, zero values will be excluded from the calculation of geometric means and CV% geometric mean. However, they will be included for all other summary statistics and the number of non-zero concentrations will be reported. All concentration values below the lower limit of quantitation (LLOQ) of 0.1  $\mu$ g/mL are set to zero, and will be displayed in the listings as zero and flagged. LLOQ values will be treated as zero in any calculations of summary statistics, and treated as missing for the calculation of the geometric means and their CV%. The number of non-zero concentrations will also be reported in the summary statistics. Missing values for any PK parameters will not be imputed.

#### 9.2.7. Baseline Definition

Baseline will be defined as the most recent, non-missing value prior to or on the first study treatment dose date. For laboratory data, baseline will be defined as the most recent, non-missing value from a central laboratory prior to or on the first study treatment dose date. If there are no central labs collected prior to or on the first dose date of study treatment, the most recent, non-missing value from a local laboratory prior to or on the first date of study treatment will be defined as the baseline value.

For subjects who did not receive study treatment during the study, baseline will be defined as the latest, non-missing collected value.

#### 9.2.8. Change from baseline

Change from baseline will be presented for safety data as described in Section 11. Change from baseline is calculated as:

• For records occurring after baseline: (visit value) – baseline value.

Percent change from baseline is calculated as:

• For records occurring after baseline: ((change from baseline) / baseline value) \* 100

If either the baseline or visit value is missing, the change from baseline and/or percent change from baseline is set to missing as well.

#### 9.2.9. Multiple Assessments

All data will be reported according to the nominal visit date for which it was reported (that is, no visit windows will be applied during dataset creation). Unscheduled data will only be included in "post-baseline" summaries for capturing a worst case across all scheduled and unscheduled visits after the first dose of protocol therapy.

Data from all assessments (scheduled and unscheduled), including multiple assessments, will be included in listings.

## 9.2.10. Cardiac Scan Modalities (ECHO/MUGA)

The same modality (ECHO or MUGA) for determining cardiac scan data (e.g., left ventricular ejection fraction (LVEF)) should be used to follow a subject throughout the study. The absolute change from baseline values will not be calculated for any subjects where the post-baseline value was determined by a cardiac scan modality that is different than the one used to determine baseline value.

### 9.2.11. Derived and Transformed Variables

See Section 10 in this RAP for details on analyses for objective response rate, clinical benefit, progression-free survival, overall survival and time to progression.

For pharmacokinetic parameters, between-subject coefficient of variation (CVb%) will be calculated by the following methods, where SD is the standard deviation of the PK parameter data, calculated using either the raw data (untransformed) or the natural logarithm of the raw data (transformed).

Untransformed Data: 100 \* (SD/Mean)

Transformed Data: 100 \* (square root[exp(SD)-1])

See Section 12 in this RAP for derivation of PK parameters.

#### **ECG Corrected QT Intervals**

The QTc values based on Bazett's formula is derived by QT interval / ((RR interval/1000)^1/2), where RR interval is in msec.

# 9.3. Study Time Periods

#### 9.3.1. Time in Relation to Treatment

Adverse events, serious adverse events, death, laboratory data, vitals, ECG, and ECHO/MUGA will be assigned to the study time periods defined below. Partial dates will be imputed into full dates, if applicable, for slotting data to the appropriate categories below (see Section 9.2.5). Flag variables (time in relation to study treatment) indicating the study time periods will be added to these datasets.

The overall observation period will be divided into three mutually exclusive segments:

**Pre-therapy** is defined as the time prior to the subject's first dose of study treatment.

**On-therapy** is defined as the time from first dose of study treatment to the date of the last dose of study treatment + 28 days.

**Post-therapy** is defined as any time beyond the on-therapy period.

Some datasets include the first dose day as On-therapy and some exclude the first dose date as On-Therapy. The first dose day (Day 1) is considered pre-therapy for ECOG, ECG, vital signs, liver events, lab tests, and cardiac scan. The first dose day (Day 1) is considered to be on-therapy for adverse events and concomitant medications.

All safety data (including those from the post-therapy period) will be listed and those occurring during the pre-therapy and post-therapy periods are to be flagged.

- Summary of Concomitant Medications with On-Therapy Onset: This summary will contain medications with start date after study treatment start date. In addition, any medication that was started during post-therapy (see above for definition of post-therapy) will be excluded. Include concomitant medication records where start relative to treatment in ('DURING').

# 9.4. Values of Potential Clinical Importance

#### 9.4.1. Laboratory Parameters

Reference ranges for all laboratory parameters collected throughout the study are provided by the laboratory. A laboratory value that is outside the reference range is considered either high abnormal (value above the upper limit of the reference range) or low abnormal (value below the lower limit of the reference range). Note: a high abnormal or low abnormal laboratory value is not necessarily of clinical concern. The laboratory reference ranges will be provided on the listings of laboratory data. Clinical laboratory test results outside of the reference range will be flagged in the listings.

To identify laboratory values of potential clinical importance, National Cancer Institute Common Terminology Criteria for Adverse Events (NCI-CTCAE v4.0) will be used to assign grades to the relevant laboratory parameters. NCI-CTCAE v4.0 can be found at https://ctep.cancer.gov/protocolDevelopment/electronic applications/ctc.htm#ctc 40

When reporting grade shifts for Biochemistry and haematology data, the records in the LAB dataset will be used.

For laboratory data which are not listed in the NCI CTCAE v4.0, a summary of values outside the normal range will be provided.

#### 9.4.2. ECG Parameters

The following criteria will be used to flag electrocardiogram (ECG) values that are values of potential clinical importance:

To identify QTc (Bazett's) values of potential clinical importance, NCI-CTCAE v4.0 will be used to assign grades (see adverse event 'Electrocardiogram QT corrected interval prolonged'). Note that there is a slight inconsistency between CTCAE v4.0 and ICH E14 (Absolute QTc interval prolongation). It was decided to align with CTCAE for the oncology standard categories.

ECG Parameter	Potential Clinical Importance (PCI) Range	Unit
Absolute QTcB interval	<450	Msec
	≥450 to <480 (Grade 1)	
	≥480 to <500 (Grade 2)	
	≥500 (Grade 3)	
Absolute QTcF interval	<450	Msec
	≥450 to <480 (Grade 1)	
	≥480 to <500 (Grade 2)	
	≥500 (Grade 3)	
Increase from baseline	Increase of $\geq 30$ to $< 60$	Msec
QTcB	Increase of $\geq 60$	

The following criteria will be used to flag other ECG values that are values of potential clinical importance:

ECG Parameter	Potential Clinical Importance (PCI) Range	Unit
PR interval	<110 (L) and >220 (H)	Msec
QRS interval	<75 (L) and >110 (H)	Msec

Normal values per age group for QTcB and QTcF, derived from the 2nd and 98th percentile values in healthy children will be used to identify the values out of normal ranges within each age group.

Age group	0-1 month	1-3 month	3-6 month	6-12 month	1-3 years	3-5 years	5-8 years	8-12 years	12-16 years
QTcB (ms) Boys	413 (378, 448)	419 (396, 458)	422 (391, 453)	411(37 9, 449)	412 (383, 455)	412 (377, 448)	411(37 1, 443)	411(37 3, 440)	407 (362, 449)
QTcB (ms) Girls	420(37 9, 462)	424(38 1, 454)	418 (386, 448)	414(38 1, 446)	417(38 1, 447)	415(38 8, 442)	409 (375, 449)	410 (365, 447)	414(37 0, 457)

Data shown above as median  $(2^{nd} \text{ percentile}, 98^{th} \text{ percentile})$ 

#### 9.4.3. Vital Signs

#### Heart rate:

To identify heart rate values of potential clinical importance, NCI-CTCAE v4.0 will be used to assign categories that align with the grades for 'Sinus bradycardia', 'Sinus tachycardia', 'Supraventricular tachycardia', and 'Ventricular tachycardia'.

Normal values per age group for heart rate, derived from the values in healthy children will be used to identify the values out of normal ranges within each age group. The following criteria will be used to flag vital sign values that are values of potential clinical importance:

Age group	0-1 month	1-3 month	3-6 month	6-12 month	1-3 years	3-5 years	5-8 years	8-12 years	12-16 years
HR (bpm) Boys	160(12 5, 190)	152(125 , 185)	134(110 , 165)	128(105 , 165)	119(95 , 155)	98(75, 125)	88(60 , 115)	78(55 , 100)	73(50 , 100)
HR (bpm) Girls	155(13 5, 215)	154(125 , 200)	139(120 , 190)	134(105 , 185)	128(95 , 180)	101(80 , 125)	89(70 , 115)	80(60 , 110)	76(50 , 100)

Data shown above as median (lower limit of normal, upper limit of normal) **Blood pressure:** 

To identify blood pressure values of potential clinical importance, NCI-CTCAE v4.0 will be used to assign categories that align with the grades for 'Hypertension'.

Vital Sign Parameter	Potential Clinical Importance (PCI) Range	Unit
Increase from baseline	≥120 to <140 (Grade 1)	mmHg
Systolic Blood Pressure	≥140 to <160 (Grade 2)	
	≥160 (Grade 3)	
Increase from baseline	≥80 to <90 (Grade 1)	mmHg
Diastolic Blood Pressure	≥90 to <100 (Grade 2)	
	≥100 (Grade 3)	

To identify blood Pressure >95th percentile for specific age, gender and percentile of height, refer to Protocol appendix 5 Blood pressure Levels for children.

#### Weight (kg):

The weight values of potential clinical importance will be increase  $\geq 10\%$  or decrease  $\geq 10\%$  from baseline weight.

#### **Temperature:**

To identify temperature values of potential clinical importance, NCI-CTCAE v4.0 will be used to assign categories that align with the grades for 'Hypothermia' and 'Fever'.

Vital Sign Parameter	Potential Clinical Importance (PCI) Range	Unit
Increase from baseline	Increase to $\geq 38$	Degrees C
temperature		
Decrease from baseline	Decrease to ≤35	Degrees C
Diastolic Blood Pressure		

